## 10. SAFETY MONITORING

### 10.1 Adverse Events

All aspects of the study will be monitored by authorized individuals in compliance with Good Clinical Practice (GCP) and applicable regulations. Refer to the Safety Management Plan for additional details.

An adverse event in this study will be defined as any unfavorable and unintended sign or symptom temporally associated with the use of the TENS units, falls while performing the Sit and Stand Test during Research Homework or physical therapy exercise, changes in health status that would impact ability to use the

intervention TENS, or hospitalizations/Emergency Department visits. Pain associated with physical therapy treatment may worsen during the study but will not be classified as an AE.

Anticipated adverse events with TENS use include:

- Skin rash or irritation from electrodes
- Anxiety, itchiness, nausea or pain with TENS

## **10.2 Assessment and Recording of Adverse Events**

The study team may contact the participant when an adverse event has been reported to collect further information on the AE, if needed. The team will determine if the adverse event is serious, related to TENS treatment, and if any action needs to be taken, for example, discontinue TENS use, or if further reporting to regulatory authorities is necessary.

Pregnancy: Pregnancy itself is not regarded as an AE. However, TENS is not recommended for use during pregnancy and the participant will be withdrawn from treatment and the outcome of all pregnancies that occur during paternal or maternal exposure to study device (spontaneous miscarriage, elective termination, normal birth or congenital abnormality) must be followed up and documented even after the participant has been withdrawn from treatment.

## **10.3 Management of Unanticipated Problems**

Unanticipated problems will be defined as unexpected adverse clinical symptoms related to TENS or electrode use. These will be reported as “other” TENS-related AE on the CRF and will be reviewed at each DSMB meeting. If unanticipated TENS-related AE are uncovered that occur in >5% of enrolled participants, the consent form will be modified, and the AE will be specifically queried on the AE CRF going forward. Participants who have completed the study will be notified of any newly recognized TENS-related AE.

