Approximately 450 participants will be enrolled at 25-35 practice sites: half of the clinics will be randomized to TENS and the other half of the clinics will be randomized to no TENS.

Inclusion Criteria:

1. Age 18 or above
2. Clinician diagnosis of FM
3. Referred for land-based PT
4. Referred for treatment for FM or chronic pain (pain lasting more than 3 months)
5. Able to provide informed consent
6. Fluent in reading English
7. Willing to use TENS

Exclusion Criteria:

1. Contraindications to TENS use (See Appendix 1 for Precautions and Contraindication references):
 - a. Pacemaker, defibrillator, implanted neurostimulator or implanted device
 - b. Epilepsy
 - c. Currently pregnant or plan to become pregnant in the next 6 months
 - d. Allergic reaction to patches with gel
 - e. Current treatment for cancer
2. Currently enrolled in another pain control study.
3. Use of TENS within the last 30 days.
4. Clinically unstable medical or psychiatric issues

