5.4 Prohibited Concomitant Interventions

5.4.1 Prohibited Interventions

Participants enrolled in a clinic randomized to no TENS will be asked to not use TENS therapy during the first 60 days of study participation. After the 60-day collection of the primary endpoint, participants in no TENS clinics will be given TENS units with instructions on how to use the device.

Participants will not be required to change any of their prescribed medications during the study and no specific medications will be prohibited.

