8 MANAGEMENT OF UNANTICIPATED PROBLEMS

Unanticipated problems will be defined as unexpected adverse clinical symptoms related to TENS or electrode use, or to specific unexpected non-TENS adverse events as identified in Section 7.1. These will be reported on the adverse event CRF and will be reviewed at each

DSMB meeting. If unanticipated AE are uncovered that occur in >5% of enrolled participants, the consent form will be modified, and the AE will be specifically queried on the AE CRF going forward. Participants who have completed the study will be notified of any newly recognized TENS-related AE.

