## 4. ENROLLMENT & RANDOMIZATION

Participants with fibromyalgia will be enrolled in outpatient physical therapy clinics: half of the clinics will be randomized to TENS+PT and the other half will be randomized to PT only. At each site, individualized PT treatment specified by the physical therapist alone or with TENS will be applied during each visit. Participants in the TENS+PT intervention clinics will receive TENS units and electrodes at baseline to be applied to the cervical and lumbar regions. They will take the units home and bring the units back to their PT clinic visits with instructions for use at home while active and during their exercises. The physical therapist at each clinic will complete routine documentation of treatment that will include the patient-specific functional scale (PSFS) at the intake visit and approximately monthly intervals.

This will be a cluster randomized pragmatic trial. A stratified randomization procedure by healthcare system and size of clinic will be used to randomize clinics to either TENS+PT or PT alone. Half of the clinics will be randomized to TENS+PT and the other half of the clinics will be randomized to PT only.

We hypothesize that using TENS in a PT setting is feasible and that FM patients using TENS in addition to their PT will have reduced movement-evoked pain and other symptoms and are more likely to reach their therapeutic goals and reduced medication use compared to those patients in the PT alone group.

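### The 5% trigger for unanticipated TENS-related events divides by everyone enrolled, not everyone given TENS. This delays it modestly, mostly early in accrual, and the two documents disagree on which events count.

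*SAP*

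**What the plan says.** SAP 10.3 defines unanticipated problems as unexpected clinical symptoms related to TENS or the electrodes. When such events "occur in >5% of enrolled participants", the consent form is changed and the event gets its own query on the form. Protocol 8 has the parallel rule: "If unanticipated AE are uncovered that occur in >5% of enrolled participants, the consent form will be modified". Its definition is wider, because besides TENS-related symptoms it extends to unexpected events unrelated to TENS: "or to specific unexpected non-TENS adverse events as identified in Section 7.1".

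On exposure, the SAP (section 4) states that "half of the clinics will be randomized to TENS+PT and the other half will be randomized to PT only". Under Protocol 5.4.1, participants at no-TENS clinics "will be asked to not use TENS therapy during the first 60 days of study participation". Protocol 6.2.5.1 places their first TENS session at about Day 65 (window -5/+15 days), and Protocol 5.1 then gives them about 120 days of use.

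On anticipated events, Protocol 7.1 names skin rash or irritation and pain. SAP 10.1 names skin rash or irritation and then "Anxiety, itchiness, nausea or pain with TENS", which adds three items.

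Both documents send these events to every DSMB meeting, whether or not 5% is reached.

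**The concern.** A rate of TENS-related events is meaningful among people who have used TENS. PT-only participants cannot contribute a study-TENS event before about Day 65, and those who drop out by Day 60 never can, yet all of them stay in the denominator. The error runs in one direction, towards acting late. It is largest early in accrual, when a consent change would reach the most future participants.

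The numerator is also unsettled. An unexpected non-TENS event that falls under Protocol 8 counts towards the trigger there but not under SAP 10.3. TENS-related nausea, itchiness or anxiety is absent from the Protocol's anticipated list but present in the SAP's. SAP 10.3 also says that unanticipated events will appear under the form's other category, whereas the form in Protocol 7.1 gives anxiety, itchiness and nausea their own boxes. A count of the other entries alone would therefore miss events that are unanticipated on the Protocol's list. Two people working from different documents could disagree on whether the trigger had been met.

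**Working it through.** **Inputs from the documents**
- Enrolment: "Approximately 450 participants will be enrolled at 25-35 practice sites" (Protocol synopsis), with half the clinics in each arm. Equal arms of 225 are an assumption.
- Recruitment over 30 months (Protocol 6.2). Uniform accrual, 450/30 = 15 per month, is an assumption.
- First control-arm TENS session at about Day 65. The first scheduled adverse event query after it is Day 90 (Protocol 7.1). Both lags are used.
- Dropout of up to 24% by Day 60 (Protocol 9.3, SAP 9). The plan's own figure reproduces: 450 × (1 − 0.24) = 342. The share of controls reaching TENS, k, is therefore taken as 0.76 to 1.00.
- TENS-arm participants count as exposed from Visit 2, when units are handed out.

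**Step 1: user rate equivalent to 5% of enrolled.** With T days since the start of accrual, T no greater than 913 (30 months), and lag L:
- Enrolled = 450 × T/913
- Exposed = Enrolled/2 + k × 225 × max(0, T − L)/913
- Equivalent user rate = 0.05 × Enrolled/Exposed

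Example at month 6 (T = 182.6, 90 enrolled):
- k = 1, L = 65: exposed = 45 + 225 × 117.6/913 = 74, and 4.5/74 = 6.1%.
- k = 0.76, L = 90: exposed = 45 + 0.76 × 225 × 92.6/913 = 62, and 4.5/62 = 7.2% (unrounded 62.3).

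| Time | Enrolled | Exposed | User rate at the trigger |
|---|---|---|---|
| Month 2 | 30 | 15 | 10.0% |
| Month 3 | 45 | 23–29 | 7.8%–9.9% |
| Month 6 | 90 | 62–74 | 6.1%–7.2% |
| Month 12 | 180 | 142–164 | 5.5%–6.4% |
| Month 24 | 360 | 300–344 | 5.2%–6.0% |
| Month 30 | 450 | 379–434 | 5.2%–5.9% |
| All controls past Day 90 | 450 | 396–450 | 5.0%–5.7% |

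**Step 2: participants needed at full enrolment.** More than 5% of 450 (22.5) means 23. With k = 0.76, exposed = 225 + 0.76 × 225 = 396, and more than 5% of 396 (19.8) means 20. With k = 1 all 450 are exposed, and both bases need 23.

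**Step 3: participants needed at 100 enrolled.** This point is reached at 100/15 = 6.7 months. About 32 people enrolled in the last 65 days (15 × 65/30.4), so 68 enrolled earlier, 34 of them controls. Exposed = 50 + 34 = 84 for k = 1, or 50 + 0.76 × 34 = 76. The current rule needs 6, which is 6/84 = 7.1% to 6/76 = 7.9% of users. An exposed base needs 5 (more than 4.2) or 4 (more than 3.8).

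**The case against.** A reader might infer that the rule fires only near a 10% rate among users, from 23/225 = 10.2%, or that at 100 enrolled it needs 6 of 50, or 12%. Both figures treat PT-only participants as never exposed. The trigger has no Day 60 cut-off, and controls go on to use TENS and contribute events. If 7% of users truly had the event, the binomial probability of reaching 23 is 96% with 450 exposed and 85% with 396. It would be only 4.5% if exposure were confined to 225. About 10% describes the first two to three months, not most of a 30-month accrual.

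The rule's reach is also limited. It governs a consent edit and a form query. The DSMB reviews these events at each meeting regardless, the study team assesses reported events for seriousness and relatedness, and the form already takes free text. In SAP 10.3 the sentence on notifying participants who have completed the study is not tied to the 5%. Neither document derives the 5% or says that it means 5% of users, so it can be read as an administrative threshold. These points stand and keep the severity low. They do not explain why people without TENS belong in the base of a TENS-related rate.

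For the non-TENS events in Protocol 8, enrolled is a sensible base, because both arms can have them. Replacing the denominator throughout that section would be wrong.

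Both anticipated-event lists are introduced as inclusive, and the SAP's three extra items already have boxes, so adding a query would be moot for them. The consent change would not be, and the disagreement over non-TENS events remains.

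**Conclusion.** The denominator is mismatched to TENS-related events, and the mismatch always delays action. Its size is modest: the 5% rule corresponds to about 10% of users in the first two to three months, about 6% to 7% at month 6, and about 5% to 6% from month 12 on. In counts, the gap is one or two participants at 100 enrolled and at most three at full enrolment. These figures rest on uniform accrual, equal arms, all TENS-arm participants receiving units, and 76% to 100% of controls reaching TENS. If 24% in both arms were never exposed, the figure at full enrolment would be 0.05/0.76 = 6.6%.

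The documents do not support a claim that the rule acts at twice its stated rate through most of accrual, or that safety oversight by the DSMB is weakened. The conflict between Protocol 8 and SAP 10.3 over which events count is plain in the text and needs no assumption. Overall this is a cheap improvement of low severity.

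**What to change.** - Keep the 5% figure. In SAP 10.3 and Protocol 8, for TENS-related events, define the denominator as participants who have received study TENS by the review date: the TENS arm from Visit 2 and the PT-only arm from the Day 65 session.
- Keep enrolled participants as the denominator for the non-TENS events in Protocol 8.
- State in both documents whether non-TENS events count towards the trigger.
- Use one anticipated-event list in Protocol 7.1 and SAP 10.1, and say which entries on the form feed the count, so that the numerator is the same under either document.

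The exposed count can come from the TENS unit accountability log (Protocol 5.3) and the record of completed Day 65 visits (Protocol 6.2.5.1). The cost is a sentence or two in each document and one extra denominator in DSMB reports. The trigger may be met slightly earlier.
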